9.3.12 SUPPLEMENTAL BPN USE

Supplemental BPN will be provided utilizing CAM2038 q1w 8 mg SC injection only in Phase 2. Supplemental BPN will be allowed at maximum of one SC injection per month (in between two scheduled clinic visits).

Percentages of subjects who require supplemental uses and total number of supplemental use episodes will be summarized.

9.3.13 ADDITIONAL SUPPLEMENTAL COUNSELING

Percentages of subjects who required additional unscheduled visits to obtain counseling to manage withdrawal symptoms or desire to use illicit opioids during each of the two phases as well as during the study will be summarized. In addition, number of unscheduled visit to obtain such counseling during each of the two phases as well as during the study will also be summarized.

9.3.14 MEASURES OF MORNING NEED TO USE/DESIRE TO USE (VAS)

Measures of VAS scores include Morning Desire to Use VAS and Morning Need to Use VAS, will be administered using unipolar 100 mm VAS (“In the past week/month, how intense has been your average desire/need to use “drug name?”, where 0 = No desire to use and 100 mm= Strongest possible desire, and from 0=No need to use and 100 mm=Strongest possible need, respectively). They will be measured at baseline and some selected post baseline visits (For more detail, please refer to Table 3, Schedule of Assessments, in Section 10 of the protocol, TRIAL PROCEDURES AND ASSESSMENTS).

Changes from baseline in the above VASs will be derived by subtracting the baseline values from the post-baseline values, thus, negative changes are indicative of improvement. Changes from baseline in measurements of craving will be analyzed via Analysis of Covariance (ANCOVA) model with treatment and baseline effects. Treatment effects and treatment differences will be estimated. The two-sided 95% confidence intervals the treatment differences will be presented. In this primary analysis, missing values will be imputed using Last Observation Carried Forward (LOCF) method.

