ⁱ It is the Investigator’s responsibility to understand and comply with all laws and regulations that apply to HIV, Hepatitis B, and Hepatitis C and testing of blood. Hepatitis B/C and HIV testing is required unless a site’s IRB prohibits such testing.

Trial Period/Phase:	Screening	Phase 1 (Weekly Visits)							
	Month:	-1	M1				M1-3		
	Week:	-3 to -1	W1				W2-W11		W12
	Day:	-21 to -1	D1 ^a	D2	D3	D4	D5-7	D8	Weekly ^b
Dispense Treatment Identification Card		X							
Urine Toxicology	X	X					X	Weekly	X
Illicit Drug Use Self-Report	X	X					X	Weekly	X
SOWS, COWS, VAS ^j	X	X	X		X	(X)	X	Weekly	X
C-SSRS ^k	X	X	X		X	(X)	X	Weekly	X
Measurement of Morning Desire to Use/Need to Use							X	Weekly	X
SL BPN or SL placebo dispensing		X	X		X	(X)	X	Weekly	X
SL BPN or SL placebo administration ^l		X	X	X	X	Daily	X	Daily	X
CAM2038 q1w or placebo SC injection ^m		X			X	(X)	X	Weekly	X
Psychosocial Counseling		X					X	Weekly	X
Adverse Events ⁿ	X	X	X		X	(X)	X	Weekly	X
Concomitant Medications/Procedures	X	X	X		X	(X)	X	Weekly	X
On-site visits	X	X	X		X	(X)	X	Weekly	X

Abbreviations: BMI=body mass index; BPN=buprenorphine; COWS=Clinical Opiate Withdrawal Scale; C-SSRS=Columbia Suicide Severity Rating Scale; D=day; DSM-V= Diagnostic and Statistical Manual of Mental Disorders – Fifth Edition; ECG=electrocardiogram; HIV=human immunodeficiency virus; M=month; SC=subcutaneous; SL=sublingual; SOWS=Subjective Opiate Withdrawal Scale; VAS=visual analogue scale; W=week (X) indicates as needed based on the individual subject.

^j SOWS/COWS/VAS will be completed each time the subject visits the clinic, as needed based on titration and dosage adjustment. On Day 1, COWS, SOWS and VAS will be completed before the test dose is administered (baseline). COWS will also be completed after the test dose on Day 1 to evaluate tolerability, and on Day 2.

^k Screening version at Visit 1 (Screening), Since Last Visit version at all subsequent visits.

^l Not to exceed 24 mg SL BPN (or placebo) per day, this administration will be done at home.

^m Not to exceed 32 mg CAM2038 q1w (or placebo) per week.

ⁿ Any spontaneously reported adverse event will be recorded after the subject signs the informed consent form. In addition, adverse events will be elicited using a non-leading question each time the subject visits the clinic.

Table 4 Schedule of Assessments: Phase 2 (Monthly Visits) and Follow-up

Trial Period/Phase:	Phase 2 (Monthly Visits)						Follow-up			
	Month:	M4		M5		M6		M7		

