10.2. Eligibility Review and Randomization

At screening, the Investigator or designee must document that the subjects meet each individual criterion (as outlined in Section 8.1 and 8.2) via a signed note or eligibility and clinical stability checklist. Signatures on these documents must be dated on or before the date of randomization in Phase 1 (Day 1). Prior to randomization, a re-check of the eligibility criteria will be performed and tolerability of the 4 mg SL BPN test dose will be confirmed.

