10.3.7. Measures of Morning Desire to Use/Need to Use

Starting on Day 8 (Week 2), subjects will be asked if they have felt desire or need to use opioids in the mornings since their last visit, and if so, how many mornings and how severe the desire/need has been (average severity of desire/need on a scale from 0 to 100).

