6.1 DEFINITION OF BASELINE

Unless otherwise stated, the last observed measurement prior to or on the date of randomization will be considered the baseline measurement. If multiple observations are made during baseline, the baseline will be defined as average of the observations obtained during the baseline phase.

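### The change-from-baseline ANCOVA for morning desire/need to use cannot be carried out as written, because the measure is first collected on Day 8, a week after randomization

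*SAP*

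**What the plan says.** SAP 9.3.14 covers the Morning Desire to Use and Morning Need to Use scales. On timing it says "They will be measured at baseline and some selected post baseline visits", and it sends the reader to protocol Table 3 for details. On derivation it says "Changes from baseline in the above VASs will be derived by subtracting the baseline values from the post-baseline values". The model is an "Analysis of Covariance (ANCOVA) model with treatment and baseline effects", with missing values filled by LOCF. SAP Appendix B lists matching change-from-baseline outputs: Tables 14.2.17.1 and 14.2.17.2, and Figures 14.1.5.3 and 14.1.5.4.

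Unless a section states otherwise, SAP 6.1 applies: "the last observed measurement prior to or on the date of randomization will be considered the baseline measurement". Section 9.3.14 states no other baseline.

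Protocol 10.3.7 describes collection differently: "Starting on Day 8 (Week 2), subjects will be asked if they have felt desire or need to use opioids in the mornings". Subjects who answer yes are then asked on how many mornings, and how severe the desire or need was on average, on a 0 to 100 scale. The recall period runs from the previous visit.

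**The concern.** The baseline value enters the planned analysis twice: it is subtracted to form the outcome, and it is the covariate. If it was never collected, neither can be formed and the model has no usable records.

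The practical risk is that whoever programs the analysis has to invent a baseline or a different model. If that happens after unblinding, the result is no longer pre-specified. The measure has some interest of its own, since protocol 5.3 names a possible reduction in morning cravings among the potential advantages of the depot products.

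**Working it through.** No sample size, power or error-rate figure is involved. The check sets the collection schedule against the baseline rule.

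1. **Date of randomization.** Protocol 7.1.2 and 10.2 place it on Day 1, after the test dose has been tolerated.
2. **Latest admissible baseline.** By SAP 6.1, this is Day 1.
3. **First collection, protocol text.** Section 10.3.7 gives Day 8 (Week 2).
4. **First collection, schedule.** In protocol Table 3 the row "Measurement of Morning Desire to Use/Need to Use" has no mark at Screening, D1, D2, D3, D4 or D5-7. Its first mark is at D8, followed by the weekly visits and Week 12. The extracted table could have lost its alignment, so I compared this row with the urine toxicology row. That row has marks at Screening and D1, four empty cells, and then a mark at D8. The morning row has six empty cells before its first mark, which puts that mark in the same D8 column. Text and table therefore agree independently.
5. **Gap.** Day 8 − Day 1 = 7 days. By then subjects have had the Day 1 and Day 4 injections and a week of sublingual tablets (protocol 9.1.1).
6. **Count.** Scheduled morning measurements on or before Day 1: 0. Expected subjects with a baseline under SAP 6.1: 0 of about 380.

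Three ways of rescuing the analysis were considered.

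- **LOCF.** It carries an earlier value forward, so it cannot supply a value from before the first collection.
- **The averaging rule in SAP 6.1.** It applies when several baseline observations exist. Here there are none.
- **The ordinary Desire/Need VAS.** Table 3, footnote j, does give this a Day 1 baseline before the test dose. But protocol 10.3.3 asks there for the worst or strongest desire or need since the last scheduled visit, whereas 10.3.7 asks for average severity in the mornings. Subtracting one from the other would not give a change in either. SAP 9.3.14 also refers to the morning scales themselves when it defines the change.

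Two features of the instrument bear on any replacement analysis.

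- **Severity is conditional.** It is asked only of subjects who report some morning desire or need. Without a score for a negative answer, a severity analysis would compare only those still reporting desire or need, a subset formed after randomization that treatment can alter.
- **The recall period changes.** It is nominally 7 days between weekly visits and 28 days between monthly ones. Seven affected mornings are 7/7 = 100% of the first and 7/28 = 25% of the second, so raw counts cannot be compared across the two phases.

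**The case against.** The strongest reply is that little depends on this. The variable is the last in the SAP 9.3 list of exploratory variables and lies outside the ordered hypotheses of SAP 9.5. The ordinary Desire/Need VAS, which does have a baseline, is analysed separately in SAP 9.3.9. The wording of 9.3.14 is close to that of 9.3.9 and still speaks of measurements of craving, so it looks like carried-over text. The protocol's own plan is sound: section 12.3.2.5 names change from baseline only for the ordinary VASs, COWS and SOWS, and lists the morning measures as a separate item. All of this stands. It limits the severity but does not remove the contradiction.

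A reader might also infer more than the documents support:

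- **That Day 8 will become the baseline and the first week's treatment effect will be adjusted away.** No section proposes this. It would be a poor choice, because the arms have by then had a week of different treatment, but it is not the plan.
- **That morning desire and need cannot be compared at all.** Only the change-from-baseline ANCOVA fails. The observed values from Day 8 onward can be compared by visit.
- **That leaving the number of mornings unanalysed is an error.** Protocol 12.3.2.5 names the morning measures in general and does not require every sub-item to be analysed. Summarising the count is optional.
- **That LOCF must give way to a mixed model.** That would be a separate choice about missing data. Dropping the baseline term is enough to cure this defect.

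**Conclusion.** Wrong as written, of minor severity. The SAP requires a baseline that the protocol does not collect, so for every subject the change score and the covariate are undefined, and the two tables and two figures cannot be produced as specified. The consequence stops at one exploratory variable. Primary, secondary and safety conclusions do not depend on it.

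This rests on two assumptions: that data collection follows protocol 10.3.7 and Table 3, and that no other SAP rule supplies a baseline for this measure. I found none. The self-report form itself is not among the documents reviewed.

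**What to change.** In SAP 9.3.14:

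1. Delete the statement that the morning measures are taken at baseline, and the derivation of change from baseline.
2. Compare the arms on observed post-baseline severity by visit, with no morning-baseline term. The Day 1 pre-dose ordinary Desire to Use or Need to Use VAS may be added as a covariate, but not subtracted. A repeated-measures model with treatment, visit and their interaction is an option, not a requirement.
3. Score a subject who reports no morning desire or need as severity 0, so that every assessed subject is included.
4. If the number of mornings is summarised, express it as a proportion of the days since the last visit.
5. Replace the past week/month 100 mm VAS description with the protocol 10.3.7 instrument: yes/no, number of mornings, and average severity from 0 to 100 since the last visit.
6. Retitle Tables 14.2.17.1 and 14.2.17.2 and Figures 14.1.5.3 and 14.1.5.4 so that they no longer refer to change from baseline.

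The cost is SAP wording and output titles. No new visit, data item or subject is needed. SAP 3.0 already requires the plan to be final before database lock and unblinding, so the change should be made by then.

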9.4 INTERIM ANALYSES

No interim analyses will be performed.

9.5 ADJUSTMENTS FOR MULTIPLICITY

There are a number of hypothesis testings that will be performed for this study. To control overall Type I error rate at 5%, a closed testing procedure will be employed (Dmitrienko 2004, Dmitrienko, Offen, Westfall 2003). Specifically, the following ordered hypotheses will be tested:

1. Superiority for CDF of percent samples that are negative for illicit opioids (Weeks 5-25);
2. Superiority for the primary efficacy variable, RR (Weeks 2-25);
3. Superiority of active treatment over the control for time to sustained abstinence after 8 weeks of treatment;
4. Non-inferiority with margin of 15% for retention rate;
5. Superiority of active treatment over the control for retention rate.

In this procedure, a comparison will be eligible for non-inferiority or superiority testing only if all previous comparisons, if any, were successfully established at the two-sided 5% significance level.

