6.0 GENERAL CONVENTIONS

Unless otherwise stated, all analyses will be performed using SAS Version 9.2 or higher and all hypothesis tests will be conducted at a two-sided significance level of 0.05. P-values will be presented with 3 decimals and p-values that are less than 0.001 will be presented as <0.001.

Continuous (non survival related) data will be summarized using descriptive statistics: number of observations (n), mean, standard deviation (SD), median, minimum, and maximum. Frequencies and percentages will be used to summarize categorical (discrete) data. Presentations of categorical data will generally suppress percentages for items where the count is zero in order to draw attention to the nonzero counts. In general, mean, standard deviation, median, minimum, maximum, and percentages will be presented with one decimal.

Unless otherwise stated, confidence intervals, when presented, will be constructed at the two-sided 95% level. For binomial variables, the 95% confidence intervals will be constructed using the normal approximation without continuity correction.

Data listings will present all data collected on case report forms (CRFs) by study drug, center, and subject number. Unless otherwise stated data will be presented by treatment and overall.

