9.1.2 PRIMARY ANALYSIS

The primary analysis of RR will be performed based on the ITT population.

An analysis of non-inferiority in the primary efficacy variable between the two treatments arms will be performed using a margin of 10% point.

Non-inferiority will be concluded if the two-sided 95% confidence interval for the difference between the probabilities of response (Active- Control) is above -0.10 . The 95% confidence interval, (LB, UB), will be derived using normal approximation:

$$\text{LB} = (P_T - P_C) - 1.96 * (1/N_T * P_T * (1 - P_T) + 1/N_C * P_C * (1 - P_C))^{0.5}, \text{ and}$$
$$\text{UB} = (P_T - P_C) + 1.96 * (1/N_T * P_T * (1 - P_T) + 1/N_C * P_C * (1 - P_C))^{0.5}, \text{ where}$$

P_T and P_C are observed proportions of the responders for the treatment and the control, respectively, and N_T and N_C are the sample sizes for the treatment and the control, respectively.

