9.2 SECONDARY EFFICACY VARIABLES

Secondary efficacy variables will include:

- Cumulative Distribution Function (CDF) of percent urine samples negative for illicit opioids (supported by self-reported illicit opioids use results) based on Weeks 5-25;

- Time to sustained abstinence of opioid use (supported by self-reported illicit opioids use results);
- Percent of subjects remaining in the study (retention rate);

9.2.1 CUMULATIVE DISTRIBUTION FUNCTION (CDF) OF PERCENT SAMPLES THAT ARE NEGATIVE FOR ILLICIT OPIOIDS (WEEKS 5-25)

Percent negative samples from 15 samples (9 weekly assessments obtained from Weeks 5 to 13, plus 3 monthly assessments obtained at Weeks 17, 21, and 25 and plus 3 random samples) will be calculated for each subject. Missing samples will be imputed as positive before the percentage is derived.

The null hypothesis of no difference in the CDF of the percent of urine samples that are negative for illicit opioids over Weeks 5-25 will be tested at the 5% significance level using Wilcoxon Rank-Sum test. The empirical CDF plot will be presented.

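### The SAP 9.5 testing order leaves out the primary non-inferiority test, so CDF superiority has no gate and could be claimed as confirmatory after the primary fails

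*SAP*

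**What the plan says.** Protocol 12.3.2.6 leaves it to the SAP to say how the significance level is protected across the primary and secondary endpoints. SAP 9.5 takes this up: "To control overall Type I error rate at 5%, a closed testing procedure will be employed". Its five ordered hypotheses are:

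1. "1. Superiority for CDF of percent samples that are negative for illicit opioids (Weeks 5-25"
2. "2. Superiority for the primary efficacy variable, RR (Weeks 2-25"
3. superiority on time to sustained abstinence
4. "4. Non-inferiority with margin of 15% for retention rate"
5. superiority on retention

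The rule for moving down the list is that "a comparison will be eligible for non-inferiority or superiority testing only if all previous comparisons, if any, were successfully established".

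The primary analysis is defined separately in SAP 9.1.2: "An analysis of non-inferiority in the primary efficacy variable between the two treatments arms will be performed using a margin of 10% point". It is judged on a two-sided 95% interval in the ITT population. SAP 9.2.1 says the CDF comparison "will be tested at the 5% significance level using Wilcoxon Rank-Sum test", and SAP 6.0 sets the default: "all hypothesis tests will be conducted at a two-sided significance level of 0.05".

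**The concern.** RR non-inferiority is the primary objective (SAP 4.1), yet it is not one of the five ordered hypotheses. Step 1 has no previous comparison, so the eligibility rule places no condition on it. Neither SAP 9.1.2 nor SAP 9.2.1 supplies one. The procedure therefore has two separate entry points, each at its full level: the primary test and the CDF test.

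A reader might assume that the primary comes first. The list's own practice argues against relying on that. For retention it writes out non-inferiority before superiority; for RR it writes only superiority, and places it after the CDF.

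What is at stake is what may be claimed if the trial misses its primary objective. As written, a CDF win could then be reported as confirmatory under a procedure described as controlled at 5%. The two endpoints can come apart in this design. Group 2 changes from the weekly to the monthly product at Week 13 (SAP 4.3), RR requires response in both phases (SAP 9.1), and 9 of the 15 CDF samples come from Weeks 5 to 13 (SAP 9.2.1).

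**Working it through.** **Inputs.** 190 per arm and 70% response in both arms (SAP 9.6); margin 10 points (SAP 9.1.2) or 13.5 points (SAP 9.6); critical value 1.96. The documents give no correlation between the RR and CDF statistics, so a range is assumed.

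**The plan's own figure.** The standard error is √(2 × 0.7 × 0.3 / 190) = 0.0470.
- Margin 13.5 points: Φ(0.135/0.0470 − 1.96) = 0.819. This reproduces the stated 82% and confirms that the primary is a one-sided 2.5% test.
- Margin 10 points: Φ(0.10/0.0470 − 1.96) = 0.566. With truly equal arms the primary fails in about 43% of trials, so the plan needs a rule for that outcome.

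**Which steps are exposed.** An RR lower bound above 0 is necessarily above −0.10. Enumeration agrees: of the 191 × 191 possible outcomes at 190 per arm, 15,412 have a lower bound above 0 and none of them fails −0.10. Success at step 2 therefore implies primary success, and steps 2 to 5 cannot succeed when the primary fails. Taken alone, the five-step list is a valid fixed sequence. Only step 1 is exposed.

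**Worst case.** Let Z1 be the RR non-inferiority statistic with the true difference at −10 points, and Z2 the CDF statistic with no true difference, bivariate normal with correlation ρ.
- (a) False claim favouring CAM2038: P(Z1 > 1.96 or Z2 > 1.96) = 0.025 + 0.025 − P(both). At ρ = 0 this is 0.05 − 0.025² = 0.0494.
- (b) The same, but counting CDF rejections in either direction. At ρ = 0 this is 0.075 − 0.025 × 0.05 = 0.0737.
- (c) CDF win with a failed primary: 0.025 − P(both). At ρ = 0 this is 0.0244.

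| ρ | (a) | (b) | (c) |
|---|---|---|---|
| 0 | 4.9% | 7.4% | 2.4% |
| 0.5 | 4.5% | 7.0% | 2.0% |
| 0.7 | 4.2% | 6.7% | 1.7% |
| 0.9 | 3.5% | 6.0% | 1.0% |

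The reference is 2.5% for (a) and 5% for (b). Count (a) cannot exceed 5%. If the CDF is truly 1 SE worse, (a) falls to 2.6% at ρ = 0.5; at 2 SE worse it is 2.5%.

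**Equal arms, 10-point margin.** The chance of a failed primary together with a false favourable CDF result is 1.08% at ρ = 0, 0.46% at 0.3, 0.16% at 0.5 and 0.002% at 0.8.

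**Practical size by simulation.** The following are assumptions, not document figures: logistic-normal subject propensity with SD 2 to 5, and dropout of 0 to 40% counted as positive. The runs used 190 per arm, 15 samples, the SAP 9.1 responder rule and a tie-corrected Wilcoxon test.
- RR 10 points worse at all visits, control RR 20% to 70%: the CDF statistic averaged 2.4 to 4.3 SE against CAM2038, with no CDF win after a failed primary in 14,000 runs.
- Equal arms: none in 14,000.
- Deficit in Phase 2 only: 1.4 to 1.7 SE against, none in 12,000.
- Opposite effects tuned so that the CDF difference is about nil, control RR 30%: negative samples 67.2% vs 56.9% in Weeks 5–13 and 33.7% vs 47.4% in Phase 2 (CAM2038 first). Any false claim occurred in 3.7% and 4.4% of trials in two runs, and a CDF win with a failed primary in 1.5% and 2.0%.
- The same at control RR 50% (85.6% vs 73.1%, then 54.2% vs 65.1%): 3.7% and 1.1%.
- The same at control RR 70%: a shift of 6 logits did not fully offset the deficit.
- Eighteen mixed-effect scenarios: a CDF win with a failed primary in 0% to 2.6% of trials. Some of these are true CDF effects, not errors.

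**The case against.** The strongest reply is that no claim the list permits is shown to breach the stated 5%. False claims favouring CAM2038 stay at or below 4.9%. The figures up to 7.4% count CDF rejections against CAM2038, which would not establish superiority. Both points stand. The 7.4% is not a rate of false superiority claims, and the 2.5% reference follows from two-sided testing at 0.05; SAP 9.5 does not name it as the target.

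Second, the excess is small in practice. RR and the CDF share 10 of the 15 CDF samples (Weeks 10–13 and the six Phase 2 samples) and the same missing-as-positive rule, so low correlations are unlikely. The most direct version of the divergence argument, a deficit confined to Phase 2, produced no CDF win after a failed primary. Opposite effects of the two products are needed, and Protocol 5.1.3 expects the products to be interchangeable. This also stands. The simulations rest on assumed inputs and are good only for order of magnitude.

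Third, the hierarchy is conveyed elsewhere: SAP 4.1 makes RR non-inferiority the primary objective and SAP 9.2 classes the CDF as secondary. This shows that a CDF win cannot meet the primary objective. It does not bar a confirmatory secondary claim after a failed primary, which is the question SAP 9.5 was meant to settle.

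**Conclusion.** The concern holds. SAP 9.5 is wrong as written: it claims overall control but omits the primary hypothesis, so its text does not guarantee strong control across the primary and the CDF. The gap is confined to step 1, and the level and power of the primary test are not affected.

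As a theoretical bound, the ungated pair nearly doubles the favourable false-claim rate, from 2.5% to at most 5%. That bound requires an RR difference exactly at the margin, no CDF difference and low correlation. The realistic excess is close to zero unless the weekly and monthly products differ from control in opposite directions. The case for changing the text therefore rests on the decision rule and the confirmatory status of a CDF result, and it should be settled before unblinding.

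**What to change.** In SAP 9.5, make hypothesis 1 *non-inferiority of CAM2038 to SL BPN on responder rate, margin 10 points*, and renumber the existing five as 2 to 6. Equivalently, add a sentence: *the sequence below is tested only if non-inferiority on the primary responder rate (Section 9.1.2) is established.*

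Either wording caps false claims favouring CAM2038 at 2.5% one-sided across the primary and the listed hypotheses. If the primary null is true, any claim first requires a false primary win. If it is not, the first true null reached in the sequence is tested at 2.5%.

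The cost is one line of text, with no change to data, sample size or primary power. What is given up is a confirmatory CDF claim when the primary fails, which at the 10-point margin is about 43% of trials if both arms truly respond at 70%. The CDF result could still be reported descriptively in that case.
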